6.4. Safety analysis

This analysis will be carried out on an exploratory basis and the frequency and detailed description of each adverse event will be reported.

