3.2. Specific objectives

- To compare the time between randomization and disappearance of symptoms in subjects receiving the D11AX22 molecule (ivermectin) vs. Placebo.
- To compare the time between randomization and clinical deterioration according to a 7-point ordinal scale in subjects receiving the D11AX22 molecule (ivermectin) vs. Placebo.
- To compare the clinical status on specific days of the disease, in subjects receiving the D11AX22 molecule (ivermectin) vs. Placebo.
- To compare the need and duration of hospitalization, supplemental oxygen, ICU, and duration of fever in the two study groups.
- To assess the safety of the D11AX22 (ivermectin) molecule in subjects with mild COVID-19 disease.

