4.3.7 Measurement of Security Parameters

On the day of the screening visit, all participants will have their liver enzymes measured. The research participant will not be randomized and therefore will not be included in the study if these are elevated > 1.5 times normal values.

In follow-up calls (days 2, 3, 4, 5, 8, 11, 15, and 21), research participants will be asked about symptoms that have historically been reported in subjects receiving ivermectin (uncontrollable shaking of a body part, dizziness, loss of appetite, nausea, vomiting, stomach pain or bloating, diarrhea, constipation, weakness, drowsiness, chest discomfort, swelling (face, arms, hands, feet, ankles, or lower legs), and other symptoms, pain and swelling in joints, painful and swollen glands in the neck, armpit, or groin, fast heartbeat, eye pain, blurred vision, redness or tearing, swelling (face, arms, hands, feet, ankles or calves), pain and swelling in the joints, painful and swollen glands in the neck, armpit or groin, fast heartbeat, pain in the eyes, blurred vision, redness or tearing, swelling of the eyes or eyelids, abnormal

sensation in the eyes, fever, blisters or peeling of skin, rash, hives, and itching) to complete the information requested by the data collection form. The proportion of research participants with adverse events in both arms will be compared.

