4.5 Data analysis

An interim analysis will be conducted without breaking the blind when 200 research participants have been randomized. The study will be discontinued if this analysis detects a significant treatment effect on the main objective, if it is detected that a significantly larger group of subjects withdraw from the intervention arm due to adverse events, or if no difference is detected between the two groups. Recruitment will continue while this analysis is performed.

The information will be analyzed with Stata version 14 (SE; Stata corporation, College Station, Texas). For this purpose, subjects will be grouped into 2 groups that comprise

- Group 1:** Subjects who received ivermectin
- Group 2:** Subjects who received placebo.

The baseline characteristics of the subjects will be described by descriptive analysis.

The main analysis will be by intent-to-treat. The time until the disappearance of symptoms will be determined when all research subjects reach day 21. Clinical deterioration or death before the 21st will be right censored- on the 21st. Deaths will be included unless there is strong evidence that the cause of death was not associated with COVID-19. The time until the disappearance of symptoms will be presented in a Kaplan-Meier curve and will be compared with the log-rank test. Hazard Ratios will be calculated with their 95% confidence interval through a Cox proportional-hazards model.

¹ 76 subjects included in the study had errors in the enlistment of the investigation product consecutively for three weeks, and will be excluded from the primary analysis.

Secondary outcomes and adverse events in each of the groups will be expressed by absolute and relative frequencies with their corresponding 95% confidence interval. For the univariate analysis in the quantitative variables, statistical parameters of central tendency and dispersion (means and standard deviations) will be described if the variable has a normal distribution. In case of not having a normal distribution, medians and interquartile ranges will be described. The qualitative variables will be measured and analyzed through proportions with their corresponding 95% confidence interval.

To determine the efficacy of the intervention in secondary outcomes, a bivariate analysis will be performed, evaluating the association of treatment, demographic and clinical variables with the different outcomes.

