4.3. Safety outcomes

-Proportion of subjects who develop adverse events and serious adverse events associated with the study drug: patients who during follow-up report episodes of uncontrollable

tremor, dizziness, loss of appetite, nausea, vomiting, stomach pain, bloating, diarrhea, constipation, weakness, drowsiness, chest discomfort, edema (face, arms, hands, feet, ankles or calves), pain and swelling in the joints, painful and swollen glands in the neck, armpit or groin, fast heartbeat, eye pain, blurred vision, redness or tearing, swelling of the eyes or the eyelids, abnormal sensation in the eyes, fever, blistering or peeling of the skin, rash, hives, and itching.

-Proportion of subjects who required discontinuation of medication due to adverse events.

5. Study population and subgroup analysis

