6.2. Secondary outcomes

Secondary outcomes, hospitalization requirement, ICU or oxygen supplementation and deterioration in more than two points on the scale of clinical results will be analyzed through a Kaplan Meier estimate. Hazard ratio will be estimated by Cox proportional-hazard model. In addition, a logistic regression model in which each secondary outcome will be considered as the dependent variable (1: Event, 0: No event) and the intervention groups as the independent variable (1: ivermectin, 0: Placebo) will be used.

For each outcome, the odds ratio (OR) and its respective 95% CI will be reported. An OR > 1 is indicating favorable results in favor of placebo and an OR <1 in favor of ivermectin. In case of low frequency of individual outcomes, a combined variable will be created using need for hospitalization (general floor or ICU) and need for oxygen (by nasal cannula or mechanical ventilation) and will be analyzed using a logistic regression model reporting the OR with its 95% CI.

Evaluation of the effect of the treatment in each study visit using the 8-point ordinal scale will be estimated using the proportional OR with its respective 95% CI with an ordinal logistic regression. In this step, the 8-point ordinal scale will be inverted in its score, where 0 will correspond to death and 7 to a subject without symptoms. Thus, a proportional OR > 1 will indicate an effect in favor of ivermectin. The 95% confidence interval of the median difference in duration of fever and length of hospitalization or oxygen use will be estimated by bootstrap estimators.

6.3. Sensitivity Analysis and Modification of the Effect for the Primary outcome.

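### SAP 6.4 plans only per-event adverse event frequencies and names no between-arm measure, although protocol 4.3.7 promises a comparison of the arms

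*Supplement*

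**What the plan says.** The current protocol lists among its specific objectives (3.2): "To assess the safety of the D11AX22 (ivermectin) molecule in subjects with mild COVID-19 disease". Section 4.3.7 describes the symptom questions asked at the follow-up calls and ends: "The proportion of research participants with adverse events in both arms will be compared". It does not say by what measure. Section 4.1.5.2 places two adverse event proportions (events associated with the study drug, and discontinuation for adverse events) among the secondary outcomes.

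Protocol 4.5 then says: "Secondary outcomes and adverse events in each of the groups will be expressed by absolute and relative frequencies with their corresponding 95% confidence interval". On the contrast between arms it offers only this: "To determine the efficacy of the intervention in secondary outcomes, a bivariate analysis will be performed". That sentence goes on to the association of treatment and other variables with the outcomes, and names no effect measure or interval.

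The latest SAP (PAE 1.0) keeps safety apart from the secondary outcomes. Section 4.3 defines "Proportion of subjects who develop adverse events and serious adverse events associated with the study drug" and "Proportion of subjects who required discontinuation of medication due to adverse events". The analysis is in 6.4, which consists of one sentence: "This analysis will be carried out on an exploratory basis and the frequency and detailed description of each adverse event will be reported". The Cox and logistic models of SAP 6.2 are introduced for "Secondary outcomes, hospitalization requirement, ICU or oxygen supplementation and deterioration in more than two points on the scale of clinical results". Safety is not named there.

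**The concern.** The documents define subject-level proportions and promise a comparison, but the section that should deliver it describes a listing by event. Followed literally, SAP 6.4 puts more than 20 symptom frequencies side by side, with no stated estimate of how far the arms differ on any safety outcome and no interval around it.

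Two things are at stake. First, without an interval for the difference, a small observed gap can be taken as reassurance when the trial cannot exclude a sizeable excess. Protocol 5.1 already states that adverse events are not anticipated, so that reading would come easily. Second, an excess spread over many symptoms need not stand out in any single row, whereas a count of subjects with at least one event could show it.

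**Working it through.** **Is there a planned figure to reproduce?** None for safety. The only sample size argument concerns symptom resolution, and it reproduces. Freedman's formula for a hazard ratio of 1.4, 80% power and two-sided alpha 0.05 (two-sided is assumed) gives (1.960 + 0.842)² × (2.4/0.4)² = 7.85 × 36 ≈ 283 events, against 290 stated. Total size: 390/0.98 ≈ 398, and 398 + 76 = 474, against 476 stated.

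**Denominator.** 476 - 76 = 400 subjects outside the product error; at 1:1 this is about 200 per arm. This is the denominator used below.

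**What each section delivers**

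| Section | Unit | Between-arm measure | Interval for the difference |
|---|---|---|---|
| Protocol 4.3.7 | participants | comparison promised, measure not named | none |
| Protocol 4.5, frequencies | per group | none | none (within-group CI only) |
| Protocol 4.5, bivariate analysis | outcomes, framed as efficacy | not named | none |
| SAP 4.3 | subjects | none (definitions) | none |
| SAP 6.2 | secondary outcomes; safety not named | OR, HR | yes, but not stated for safety |
| SAP 6.4 | each adverse event | none | none |

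**Do within-group intervals suffice?** With equal rates p and n per arm, the half-width for one proportion is 1.96 × √(p(1-p)/n), and for the difference 1.96 × √(2p(1-p)/n), which is √2 times larger. At n = 200 and assumed rates:

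| p | one arm | difference |
|---|---|---|
| 1% | 1.4 points | 2.0 points |
| 5% | 3.0 | 4.3 |
| 10% | 4.2 | 5.9 |
| 20% | 5.5 | 7.8 |
| 50% | 6.9 | 9.8 |

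Per-arm intervals can also mislead when compared by eye. For an assumed 40/200 versus 24/200, the Wilson intervals are 15.0 to 26.1% and 8.2 to 17.2%. They overlap, yet the Newcombe interval for the difference of 8.0 points is 0.8 to 15.2, which excludes zero.

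**Size of the missing interval.** Newcombe's limits combine the Wilson limits (l, u) of each arm: lower = d - √[(p1 - l1)² + (u2 - p2)²]; upper = d + √[(u1 - p1)² + (p2 - l2)²]. All counts are assumptions.

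- 30/200 versus 20/200: Wilson 10.7 to 20.6% and 6.6 to 14.9%. Lower = 5.0 - √(4.29² + 4.94²) = -1.5; upper = 5.0 + √(5.61² + 3.43²) = 11.6. Result: +5.0 points (-1.5 to 11.6).
- 6/200 versus 2/200: +2.0 points (-1.0 to 5.5).
- 0/200 versus 0/200: the Wilson upper limit is 3.84/(200 + 3.84) = 1.9%, so an excess of 1.9 points is not excluded.
- A high background, 160/200 versus 150/200: +5.0 points (-3.2 to 13.1).

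**Effect of the product error on an as-assigned contrast.** The amendment log (Amendment 4) says 38 subjects randomized to placebo were given ivermectin, so that all 76 subjects in that period received it. That leaves 38 per arm affected, or 238 per arm in all. If the true risks were 15% on ivermectin and 10% on placebo (assumed), the placebo-assigned arm would show (200 × 10% + 38 × 15%)/238 = 25.7/238 = 10.8%. The difference would shrink from 5.0 to 4.2 points.

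**The case against.** The plan is not silent. The protocol lists both adverse event proportions as secondary outcomes, applies a bivariate analysis to secondary outcomes, and gives per-group intervals for adverse events. SAP 6.2 speaks of a logistic model for each secondary outcome. A statistician holding both documents could therefore reach an odds ratio for adverse events. SAP 4.3 still defines subject-level proportions, and nothing in 6.4 cancels them. Once counts and denominators are published, anyone can compute the difference. The safety analysis is openly exploratory and the trial was not sized for it.

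Much of this stands. A reader might infer that the plan gives no comparison and no precision for safety at all, or that it abandons subject-level counting. The documents do not support that: 4.3.7 commits to comparing, 4.5 gives within-group intervals, and 4.3 keeps the subject as the unit. An exploratory analysis without tests is also acceptable. The route through other sections remains ambiguous, however. The bivariate sentence is framed as efficacy and names no measure, and the SAP separates safety from the outcomes that 6.2 names.

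A further fair point is that the solicited symptoms include fever, nausea, vomiting and diarrhea, which the protocol's introduction gives as common in COVID-19. The any-event rate may be high and driven by disease, so the pooled contrast is not certain to reveal a drug effect. That is a reason to keep the symptom table beside it.

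**Conclusion.** The point holds as a gap between sections: SAP 6.4 does not name the measure needed to carry out the comparison in protocol 4.3.7 for the outcomes in SAP 4.3. No section states an estimate of the between-arm difference in adverse events with its interval. The primary analysis is unaffected.

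In size, for assumed rates of 1% to 50% and 200 per arm, the missing interval has a half-width of about 2.0 to 9.8 points. These rates are illustrations, because the documents give none. The conclusion that a per-event listing leaves this uncertainty unstated does not depend on which rate is chosen.

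The documents do not show that a harm would be missed or that a claim of safety is planned; those would be inferences beyond the text.

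**What to change.** In SAP 6.4:

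- Report, by arm, the number and percentage of subjects with at least one adverse event, at least one serious adverse event, and discontinuation for adverse events. Give each a risk difference with 95% CI (Newcombe or Miettinen-Nurminen), without formal testing. The exploratory label can stay.
- State whether the restriction to events associated with the study drug, which SAP 4.3 attaches to its first safety outcome, applies to these counts.
- Base the main contrast on subjects outside the 76 affected by the product error, and report those 76 separately by product received, so that subjects exposed to ivermectin are not counted as placebo.
- Count each subject once over the scheduled contacts: the eight calls for symptoms, and days 2, 5, 8, 11, 15 and 21 for serious events, as in the protocol's visit table.
- Keep the per-symptom frequencies as description.

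The cost is SAP wording and three risk differences from data already scheduled for collection. The downside is that the intervals will be wide and will make the safety statement less favourable.

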| Final Amendment 3 to the Study Protocol_September 16, 2020 | 
a. This specific objective was included: "To compare the time between randomization and disappearance of symptoms in subjects receiving the D11AX22 molecule (ivermectin) vs. Placebo"
 
b. The original primary outcome was changed to: "To determine the time until the resolution of the symptoms in the two study groups."
 
c. The original primary outcome becomes a secondary outcome
 | 
Less than 3% of the subjects included to date have had the primary outcome described in Amendment 2 ("To determine the time to deterioration in two or more points of the 7-point ordinal scale in the two study groups."). If this primary outcome were retained, the sample size to obtain adequate statistical power would be unattainable (more than 2000 subjects).
 
With this amendment we intend to meet the general and specific objectives with the initially proposed sample size.
 | No new ICF issued | Approved by INVIMA on November 06, 2020 |
| Final Amendment 4 to the Study Protocol_October 27, 2020 | 
a. Sample size increased to 476
 | 
After the start of the study, 38 subjects who were randomized to receive placebo were given ivermectin by mistake in the enrollment of the investigation product. This occurred consecutively over a period of three weeks, so during this period a total of 76 subjects received ivermectin and none received a placebo.
 
This situation was discussed with the independent data monitoring board. Taking into account that this is a systematic error, in which none of these participants received the randomly assigned investigation product, the exclusion of these 76 subjects from the primary analysis was decided. To preserve the planned sample of 400 subjects and thus preserve the statistical power of the study, an additional 76 participants will be included for a total of 476 participants. The 76 participants excluded from the primary analysis will complete the follow-up established by the protocol.
 | INFORMED CONSENT FORM AND GENERAL INFORMED CONSENT OF THE STUDY_Version 6.0_476 October 27, 2020 | Approved by INVIMA on November 9, 2020: |

Statistical Analysis Plan

(SAP)

| | |
|------------------------|---|
| Protocol Title | Double blind, randomized, controlled clinical trial to investigate the effectiveness of the d11ax22 molecule in adult subjects from Valle del Cauca with initial stages of infection by SARS-CoV-2/ Covid-19. |
| Acronym | EPIC |

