5.1. Populations

Intention to Treat (ITT). It is the primary population of the EPIC trial and includes all patients randomized in the study. They will be analyzed according to the group assigned at the randomization visit, regardless of whether they received the medication or not.

Per protocol (PP). All patients who were adherent to the assigned intervention at the time of randomization. In addition, it includes all patients with complete data. It will be considered as a sensitivity analysis.

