5.2. Subgroups

No subgroup analysis will be done.

6. Analysis plan

Initially, all the variables will be described according to the intervention groups in the ITT population. Variables with a normal distribution will be summarized with mean and standard deviation (SD), otherwise, they will be shown with median and interquartile range (IQR). Normal distribution assumption will be evaluated using the Shapiro Wilk test. All analyzes will be done in Stata 16.0® (StataCorp, College Station, Texas, USA).

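### The SAP gives its safety analysis no population or grouping rule, although 38 placebo-assigned patients are known to have received ivermectin, and its general rule conflicts with protocol 4.5 on where to count them

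*Supplement*

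**What the plan says.** The current SAP (PAE 1.0) defines two analysis sets in section 5.1, ITT and per protocol. Of ITT it says: "It is the primary population of the EPIC trial and includes all patients randomized in the study". On grouping it says: "They will be analyzed according to the group assigned at the randomization visit, regardless of whether they received the medication or not". There is no safety set.

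The opening paragraph of SAP section 6 gives a general rule: "Initially, all the variables will be described according to the intervention groups in the ITT population". Section 6.4, on safety, reads in full: "This analysis will be carried out on an exploratory basis and the frequency and detailed description of each adverse event will be reported". It states neither a set nor a grouping.

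The current protocol treats safety as a specific objective (3.2). Section 4.3.7 says: "The proportion of research participants with adverse events in both arms will be compared". Section 4.5 labels the two analysis groups by the product the subjects received. It then reports adverse events in each of those groups, as frequencies with 95% confidence intervals.

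The Amendment 4 entry in the protocol's summary of changes records that "38 subjects who were randomized to receive placebo were given ivermectin by mistake in the enrollment of the investigation product". During those three weeks 76 patients received ivermectin and none received placebo. The footnote to protocol 4.5 says that these 76 "will be excluded from the primary analysis", and SAP 2.2 repeats this. Amendment 4 adds that they complete the planned follow-up, so their adverse events are collected.

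**The concern.** When some patients are known to have received the other arm's product, a safety analysis has to state whether events follow assignment or exposure. This SAP acknowledges the 76 in its sample-size section, but the populations and safety sections carry no rule for them.

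If the analyst falls back on the SAP's general rule, events in 38 ivermectin-exposed patients are tabulated as placebo events. That pulls the comparison promised in protocol 4.3.7 toward no harm, and an event that occurs only on ivermectin could look non-specific. If the analyst follows the group labels in protocol 4.5, the same events appear under ivermectin. Two competent analysts could therefore produce different safety tables, each with support in the text.

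**Working it through.** **Inputs.** Total 476, allocation 1:1 (SAP 2 and 2.2). Error-window patients 76, of whom 38 were assigned placebo (Amendment 4), leaving 76 − 38 = 38 assigned ivermectin. The documents give no expected adverse-event rates and no numerical target for safety.

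**The plan's own total.** Amendment 4 adds 76 to the planned 400: 400 + 76 = 476. By the route in SAP 2.2, 390 / 0.98 ≈ 398 and 398 + 76 = 474, which is close. So 476 is a sound base for the counts below.

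**Column sizes under each reading.** An even split is assumed: 476 / 2 = 238 per arm. Correctly dispensed placebo patients: 238 − 38 = 200. All ivermectin-exposed patients: 238 + 38 = 276.

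| Reading | Basis | Ivermectin column | Placebo column | Placebo column exposed to ivermectin |
|---|---|---|---|---|
| All randomised, by assignment | SAP 5.1 with section 6 | 238 | 238 | 38 (38/238 = 16.0%) |
| By product received | Group labels in protocol 4.5 | 276 | 200 | 0 |
| The 76 left out | Primary-analysis exclusion carried over to safety | 200 | 200 | 0 |

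**Dilution under the first reading.** Let p0 and p1 be the true risks on placebo and ivermectin, with the 38 having risk p1.

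- Observed placebo-column risk = (200·p0 + 38·p1) / 238
- Observed risk difference = p1 − that value = (200/238)·(p1 − p0) = 0.840·(p1 − p0)

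The 16% shrinkage does not depend on the event rates. The effect on the risk ratio does. For a range of assumed rates:

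| Assumed placebo vs ivermectin risk | Placebo risk as tabulated | Risk difference, true → tabulated (points) | Risk ratio, true → tabulated |
|---|---|---|---|
| 5% vs 10% | 13.8/238 = 5.8% | 5.0 → 4.2 | 2.00 → 1.72 |
| 10% vs 20% | 27.6/238 = 11.6% | 10.0 → 8.4 | 2.00 → 1.72 |
| 20% vs 30% | 51.4/238 = 21.6% | 10.0 → 8.4 | 1.50 → 1.39 |
| 30% vs 40% | 75.2/238 = 31.6% | 10.0 → 8.4 | 1.33 → 1.27 |

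**An event that occurs only on ivermectin.** The chance that at least one case is listed under placebo is 1 − (1 − r)^38. For assumed r of 1%, 2% and 5%, this is 32%, 54% and 86%.

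**What leaving out the 76 costs.** It discards 76/276 = 27.5% of ivermectin exposures. If an event is never seen, the 95% upper bound on its risk is 1 − 0.05^(1/n): 1.1% with n = 276 and 1.5% with n = 200.

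**What pooling by product received costs.** The 76 came from a period with no placebo recipients. The 276 vs 200 comparison therefore mixes concurrently randomised patients with patients who have no concurrent control.

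**The case against.** A reader might infer that the plan has settled on counting the 38 as placebo patients. The documents do not support that.

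- SAP 6.4 is silent on set and grouping. The section 6 sentence opens a paragraph on means, medians and a normality test, and can be read as covering the initial descriptive step rather than the adverse-event tables.
- Protocol 4.5 contains the only text that ties adverse-event reporting to defined groups, and those groups are labelled by receipt. On that text the 38 belong under ivermectin.
- No text says that the 76 enter the safety tables. SAP 5.1 calls ITT the primary population while the 76 leave the primary analysis, so the working set might be the 400. In that case no misclassification arises.

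All of this stands, and it limits the point to an unresolved conflict. It does not remove it. The receipt labels in protocol 4.5 sit close to a statement that the main analysis is by intent-to-treat, so they may be loose drafting. Read literally, SAP 5.1 and 6 still lead to the biased table.

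It would also go too far to call the other two readings invalid. Each avoids the misclassification, and the fix below draws on both. What they lack is a statement of how the 76 are shown.

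Finally, the safety analysis is exploratory, the error is disclosed, the 76 are identifiable, and the data monitoring board was consulted. These facts lower the severity. The SAP's ITT set would also keep never-dosed patients in the denominators, but this is minor: treatment starts at the randomisation visit and no count of undosed patients is given.

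**Conclusion.** The point holds as an undefined safety population combined with a conflict between SAP 5.1/6 and protocol 4.5. It should be fixed, though it does not threaten the primary analysis.

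If the SAP's general rule is applied literally, about 16% of the placebo column is ivermectin-exposed, and any true risk difference is reported at 84% of its size. That figure rests on an even 238/238 split, on all 76 entering the tables by assigned arm, and on the 38 having the same event risk as other ivermectin recipients. The event rates used above are assumptions that show scale only. No power figure is offered, because the safety analysis is exploratory and the plan states no powered safety test.

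**What to change.** Reconcile SAP 5.1 and 6.4 with protocol 4.5:

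1. Define a safety set of all patients who took at least one dose, classified by the product actually received.
2. Make the between-arm comparison, as a risk difference with 95% confidence interval for any adverse event, any serious adverse event and each listed event, in the correctly dispensed, concurrently randomised patients (200 vs 200 if the split is even and all are dosed).
3. Show the 76 error-window patients in a separate ivermectin-exposed column, so that the descriptive ivermectin total is up to 276.
4. State that the 38 are not listed under placebo in any safety table.

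The cost is SAP wording, matching wording in protocol 4.5, and one extra table column. No new data are needed, because the 76 already complete the scheduled follow-up.
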